## ***IX. Data Analysis Plan***

The primary outcome measure is opioid consumption with and without pre-operative opioid education. By comparing the two arms we will determine the difference in opioid consumption between groups of patients who receive education and those who do not. We will also analyze opioid disposal in the two groups and compare disposal rates.

Descriptive statistics (means, medians, percentages, standard deviations, and interquartile ranges) for all variables will be computed overall and for each intervention group. The distributions of continuous variables will be evaluated for normality. If distributions are non-normal, continuous variables will be described as median (interquartile range) and compared across intervention groups using Wilcoxon-rank sum tests. Otherwise, continuous variables will be described as mean $\pm$ standard deviation and compared between intervention groups using independent t-tests. Categorical variables will be reported as frequencies(percentages) and compared between groups using the chi-square or exact test, as appropriate. To account for multiple comparisons between the three groups, p-values will be adjusted using the stepdown Bonferroni approach. We will utilize the chi-square test to determine whether there is a significantly greater proportion who (Hypothesis 1) return more than 10 tablets in Arm 2 versus Arm 1; and (Hypothesis 2) properly dispose of unused tablets in Arm 2 versus control Arm 1. If necessary, we will adjust for potential covariates using logistic regression in place of the chi-square test with the control group serving as the referent group.

A sample size estimate was performed based on previous literature and data from our pilot study that showed nearly 55% of subjects returned 10 or more out of 40 tablets.

Assuming ~55% will return 10 or more out of 40 tablets in the control group, a total of 68 subjects per group (n=136 total, with calculated 10% drop out) would provide 80% power, with an alpha level of 0.05 (2-sided test), to detect a 25% difference in the proportion who return 10 or more tabs in the brochure/video intervention group (35%).

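### The sample-size statement calls 55% versus 35% a 25% difference; it is 20 points, and 136 patients give about 61% power for it, not the stated 80%

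*Combined protocol and SAP*

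**What the plan says.** The only justification of the sample size is one sentence, which appears in the same form in V. Study Design and in IX. Data Analysis Plan. Its parts are:

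- Control rate: "Assuming ~55% will return 10 or more out of 40 tablets in the control group".
- Size and power: "a total of 68 subjects per group (n=136 total, with calculated 10% drop out) would provide 80% power", at a two-sided alpha of 0.05.
- Target effect: "detect a 25% difference in the proportion who return 10 or more tabs in the brochure/video intervention group (35", where the last figure, in brackets, is the intervention-group rate of 35%.

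VI. Study Procedures sets 1:1 allocation. IX. Data Analysis Plan names the chi-square test for the comparison of return proportions.

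**The concern.** Three printed numbers cannot all be true: a control rate of about 55%, an intervention rate of 35%, and a difference of 25%. This matters because the stated power depends on which of them was used. If 136 patients were sized for a 25-point difference, the stated 80% does not apply to the smaller difference implied by 35%. A reader of a null result would then believe that a fall from 55% to 35% had been tested with 80% power when it had not. Section VIII says the trial should inform a larger study, so a wrong planning effect could carry over into that study.

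**Working it through.** **Inputs, all from the sample-size sentence unless noted.** Control rate p1 = 0.55; intervention rate p2 = 0.35; printed difference 25%; 68 per group including 10% dropout; power 80%; two-sided alpha 0.05; 1:1 allocation (VI. Study Procedures); chi-square test (IX. Data Analysis Plan). Evaluable per group: 68 × 0.9 = 61.2, so 61.

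**The difference.** 0.55 − 0.35 = 0.20, which is 20 points. In relative terms it is 0.20/0.55 = 36%. A 25-point fall gives 30%; a 25% relative fall gives 0.55 × 0.75 = 41.25%.

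**Formulas (pooled-variance normal approximation).** With p̄ = (p1 + p2)/2:

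- n per arm = [1.960·√(2p̄(1−p̄)) + 0.842·√(p1(1−p1) + p2(1−p2))]² / (p1−p2)²
- power = Φ{ [|p1−p2|·√n − 1.960·√(2p̄(1−p̄))] / √(p1(1−p1) + p2(1−p2)) }
- enrolled per arm = n/0.9, rounded up

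**Reproducing the plan's figure: 55% versus 30%.** p̄ = 0.425, √(2 × 0.425 × 0.575) = 0.699 and √(0.2475 + 0.2100) = 0.676. Then n = (1.370 + 0.569)²/0.0625 = 60.2, so 61 per arm; 61/0.9 = 67.8, so 68 per arm and 136 in total. Power at 61 per arm is 80.5%. This matches the plan exactly.

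**The printed rate: 55% versus 35%.** p̄ = 0.45, √(2 × 0.45 × 0.55) = 0.704 and √(0.2475 + 0.2275) = 0.689. Then n = (1.379 + 0.580)²/0.04 = 95.9, so 96 per arm; 96/0.9 = 106.7, so 107 per arm and 214 in total. At 61 per arm, power = Φ[(0.20 × 7.810 − 1.379)/0.689] = Φ(0.266) = 60.5%.

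| Alternative (control 55%) | Needed per arm, evaluable | Needed per arm, enrolled | Power at 61 | Power at 68 |
|---|---|---|---|---|
| 30% (25 points down) | 61 | 68 | 80.5% | 85% |
| 35% (20 points down, as printed) | 96 | 107 | 60.5% | 65% |
| 41.25% (25% relative reduction) | 207 | 230 | 33% | 36% |
| 75% (20 points up) | 89 | 99 | 64% | 69% |
| 80% (25 points up) | 54 | 60 | 85% | 88% |

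The upward rows are included because Hypothesis 1 in IX. Data Analysis Plan expects a greater proportion in Arm 2, whereas the sample-size sentence has a lower one.

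**Does the choice of method rescue 35%?** Power for 55% versus 35% at 61 per arm is 62.0% (unpooled variance), 60.9% (arcsine), 62.6% (exact enumeration of the uncorrected chi-square), 55.4% (Fisher exact) and 53.2% (continuity-corrected). For the required size, a continuity correction gives 106 evaluable and 118 enrolled per arm, and a one-sided 0.05 test gives 76 and 85. Inflating by 1.1 instead of dividing by 0.9 gives 106 enrolled. None returns 68 per arm or 80% power.

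**The case against.** The strongest reply is that 35% is simply a misprint for 30%. The 55% control rate, the 25% difference, the 10% dropout, the 68 per group and the 80% power all fit together, and only 35% does not. On that reading the size and the power are sound and one digit is wrong. This is quite possibly what happened, and the 61% figure is conditional on the printed 35% being the intended alternative. But nothing in the documents says so, both copies carry the same figures, and a correction is needed on either reading.

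A second reply is that the control rate is only approximate. With 60% versus 35%, a true 25-point difference, power at 61 per arm is 79.7% and the required size is 69 enrolled per arm. That comes close to the plan, but it contradicts the 55% that is given both as the pilot finding and as the planning assumption, so a printed number would still be wrong.

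A third reply is that the abstract and Section VIII describe work preparatory to a larger study, and that opioid consumption, the named primary outcome, might be analysed as a continuous variable. This softens the consequence without removing it. The plan claims 80% power for the dichotomised return endpoint, and it gives no inputs from which power on a continuous scale could be worked out.

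The direction of effect is a separate inconsistency and does not help here: 20 points upward also falls well short of 80%.

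**Conclusion.** The concern holds. With a control rate of 55%, the printed 35% is a 20-point difference, and the stated 80% power does not apply to it. Power is about 61% if the planned 10% dropout occurs (61 evaluable per arm) and about 65% if nobody drops out, so the risk of missing a true effect of that size is about 40% or 35%, against the stated 20%. The stated 136 patients and 80% power are correct for 55% versus 30%. The result rests on a two-sided 0.05 comparison of two proportions with equal arms. The uncorrected methods at 61 per arm agree to within about 2 points, and the corrected or exact tests give lower power. Which printed number was intended cannot be settled from the documents.

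**What to change.** Ask the sponsor to go back to the underlying calculation, say which alternative was used, and correct the sentence in both V. Study Design and IX. Data Analysis Plan without changing the sample size:

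- **If a 25-point difference was intended,** replace 35% with 30%. The 136 patients and 80% power then stand.
- **If 35% was intended,** write 20 percentage points and restate power as about 61%. For reference, 80% power at 35% would take 107 enrolled per arm (214 in total).
- **In both cases,** call the difference percentage points and state that the power rests on 61 evaluable patients per arm.

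If the sponsor also turns the alternative upward to agree with Hypothesis 1, the figures at 61 per arm are about 85% power for 80% (25 points) and about 64% for 75% (20 points). The 25-point upward case needs only 60 enrolled per arm, so the text should then say that 68 exceeds the minimum.

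The cost is wording in two paragraphs. There are no extra patients and no new data. If 35% or any other 20-point alternative is kept, the plan must accept a less favourable power statement.
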